2.3 Patient Characteristics for High Risk of Mortality

There are a number of reports of the constellation of clinical parameters that are associated with worse outcome when individuals are infected with SARS-CoV-2. (1) As noted by Ruan and colleagues, age has a profound impact on risk of death ($P<0.001$) as does presence of comorbid illness ($p=0.0069$).(25) This was confirmed by several authors.(26) (27)(1)(6) This is especially true of cardiovascular diseases which are associated with significantly increased risk of death when they are infected with SARS-CoV-2 ($p < 0.001$) and cancer which makes sense when one considers the underlying lymphopenic milieu seen in a number of hematological malignancies and their associated therapies.(2,28)(1)(29) In the Washington experience, Comorbidities were identified in 18 cases with chronic kidney disease and congestive heart failure being the most common diseases suggesting a poor outcome.(30)

Broadly, there are several markers of inflammation that portend to a worse prognosis as well. These include presence of lymphopenia, cardiac troponin, C-reactive protein, Interleukin-6 (IL-6) and thrombocytopenia.(25)(4,26,31,32) Markers of inflammation tended to demonstrate significantly higher levels in those with severe disease or those who go on to severe disease than in those with mild disease. Gao et al reported several key findings. C-reactive protein (CRP), D-Dimer, IL-6 were all significantly higher in the severe patient populations than in those with mild disease. Specifically, they showed the level of CRP was significantly higher in the severe group than in the mild group, D-Dimer level was higher in the severe group versus the mild group and IL-6 tended to be elevated in the severe group. In fact, testing the combination of IL-6 and D-Dimer added to the sensitivity and specificity for predicting severity of disease. When combining IL-6 with D-Dimer by parallel testing, the sensitivity and specificity were 66.7% and 96.4%, respectively. The specificity was reported at 96.4% when IL-6 and D-Dimer were combined by tandem testing. (33) Others confirmed these findings, yet it is still unclear whether these solely represent the physiological response to disease or may serve as a target for treatment.(4)

Much has been proposed in relation to outcomes of COVID-19 infections in patients with cancer. There continues to be some conflicting results. Liu and colleagues found no increased mortality in 78 patients studied with cancer and SARS-CoV-2 infections.(31) Though in reporting on 1590 patients, Liang concludes that those with an underlying malignancy had a worse outcome. In fact, patients who underwent chemotherapy or surgery in the month prior had a higher risk of clinically severe events than did those not receiving chemotherapy or surgery.(34) A case fatality rate of 5.6% in patients with cancer was reported by Wu and colleagues.(1)

A common feature of COVID-19 is the presence of absolute lymphopenia. (35) This tends to predominate within the T cell subsets of both CD4 and CD8. Often, one may find a corresponding increase in the B cell subpopulation. Lymphopenia has been clearly shown to be associated with a worse outcome.(26) In fact, CD4+T and CD8+T cells decreased in nearly all the patients studied and were especially low in severe cases (177.5 and $89.0 \times 10^6/L$) compared with moderate cases (381.5 and $254.0 \times 10^6/L$). Bhatraju et al described lymphopenia occurring in around 75% of patients on admission to the ICU in the Seattle experience, where median lymphocyte count was 720 per cubic millimeter.(10) [name] and colleagues conclude that “lymphopenia is an effective and reliable indicator of the severity and hospitalization in COVID-19 patients”.(36) They go on to provide several theories as to the origin of lymphopenia, including proinflammatory effect, direct impact on lymphatic organs and presence of ACE2, a target of SARS-CoV-2, on the lymphocytes.

As noted, there are several studies that assign increased mortality related to COVID-19 amongst those who present with comorbid illnesses. However, the most poignant data seems to suggest the presence of heart disease is particularly associated with poor outcome. (37) One meta-analysis described patients with previous cardiovascular diseases were at greater risk of developing into advanced disease.(38) Personal history of hypertension in several studies seem particularly associated with worse outcomes.(4)(1) SARS-CoV-2 is thought to directly impact cardiac tissue via attachment to ACE2 receptors in the myocardium which results in cellular damage. ACE2 presence in the lungs and myocardium likely results in those two organ systems being disproportionately impacted resulting in untoward results. (39) Further, those with underlying cardiovascular disease have less reserve and this constellation results in SARS-CoV-2 infection with underlying cardiovascular disease at profound risk of mortality. Recognizing this risk and establishing clinical approach to protect this particularly vulnerable group is prudent.

It is quite interesting that patients who are active tobacco users tended to fare worse as well. (40) There are several theories but Emami suggests it is related to regulation of the ACE2 in patients who smoke tobacco compared to those who do not.

COVID-19 has had a catastrophic impact on patients and society as a whole. While herculean efforts have been undertaken to mitigate the spread of the infection, it seems that asymptomatic and mildly symptomatic patients have added to the impact globally. It is clear that patients who present in a critical state do quite poorly and many or most will die. The purpose of this study is to employ a safe therapeutic modality that can readily be accessed and use it earlier in the clinical course in high risk patients and those whose clinical picture portends to worse outcome. If able to stop this progression to critical status, it will likely provide us with the best opportunity to truly impact the morbidity and mortality of COVID-19.

3.0 RATIONALE FOR STUDY SCHEDULE

Duan and colleagues have reported excellent outcomes with the use of 200 mL convalescent plasma in the treatment of COVID-19.(24) This is administered as one unit of plasma (approximately 200 mL) over 30 to 60 minutes.

4.0 PATIENT SELECTION

4.1 Eligibility Criteria

4.1.1 Diagnosis of SARS-CoV-2 infection via RT-PCR or FDA approved testing.

4.1.2 Patients must also have the following indications for enrollment:

- i. D-Dimer > 500 ng/ml FEU **OR**
- ii. IL-6 > 5 pg/mL

With any of the following

- iii. Lymphocytes < 0.8 10^3 /ul **OR**
- iv. LDH > 700 U/L **OR**
- v. CK > 170 U/L **OR**
- vi. CRP > 1.0 mg/dl **OR**
- vii. Ferritin > 1000 ng/ml

AND one of the following:

- viii. Age over 60 years
- ix. Underlying Active Malignancy
- x. Cardiovascular Disease
- xi. Active Tobacco Use
- xii. History of Pulmonary Volume Reduction Surgery
- xiii. Hypertension

4.1.3 Prior Treatment: Patients are still eligible for this trial if active antimicrobial agents are in use. Patients are also eligible if they had been treated on COVID-19 clinical trial in the course of their disease.

4.1.4 Age \geq 18 years.

4.1.5 The effects of allogeneic plasma infusion on the developing fetus is unknown. For this reason women who are pregnant are not eligible to participate.

4.1.6 Agrees to required laboratory data collected which will include the baseline organ function and regular ongoing assessments done as part of routine care.

4.1.7 Ability to understand and the willingness to sign a written informed consent document or ability to have consent provided by Legally Authorized Representative.

4.2 Exclusion Criteria:

4.2.1 Patients who do not meet above inclusion criteria are not eligible.

4.2.2 Patients may not be receiving any other investigational agents.

4.2.3 History of allergic reactions attributed to previous transfusion history.

4.2.4 Respiratory rate >30/min

4.2.5 Blood oxygen saturation <93%

4.2.6 Partial pressure of arterial oxygen to fraction of inspired oxygen ration <300

4.2.7 Diagnosis of respiratory failure, septic shock or multiple organ dysfunction/failure

4.3 Inclusion of Women and Minorities

Both men and women of all races and ethnic groups are eligible for this trial.

5.0 DONOR INFORMATION

5.1 Eligible donors must have evidence of COVID-19 documented by

5.1.1. A laboratory test either by diagnostic test at the time of illness OR a positive serological test for SARS-CoV-2 antibodies after recovery, if diagnostic testing was not performed at the time COVID-19 was suspected. AND

5.1.2. Complete resolution of symptoms at least 14 days prior to donation.

5.2 Male donors, or female donors who have not been pregnant, or female donors who have been tested since their most recent pregnancy and results interpreted as negative for HLA antibodies.

5.3 Those who are identified as a potential donor will be referred to Kentucky Blood Center, a FDA registered (#1070402) and licensed blood establishment, and must adhere to standards as described for all potential donors per federal regulations. Convalescent plasma is collected, processed, and provided in accordance with Kentucky Blood Center SOP 11-02-005 Convalescent Plasma (Appendix 1).

5.4 ABO compatible with the patient.

5.5 If SARS-CoV-2 neutralizing antibody titers are available:

5.4.1 Neutralizing antibody titers of at least 1:160 is preferred.

5.4.2 A titer of 1:80 may be considered acceptable if an alternative matched unit is not available.

5.4.3 If a measurement of neutralizing antibody titers is not available, a retention sample from the convalescent plasma donation will be retained for determining antibody titers at a later date.

6.0 Treatment Plan

6.1 Convalescent Plasma Therapy

6.1.1. Convalescent Plasma Infusion Workflow

- Eligibility criteria reviewed and patient is eligible.
- Informed Consent from Patient or Legally Authorized Representative obtained
- Patient Registered with Kentucky Blood Center per protocol.
- Patient is Typed and Crossed per Institution protocols.

Convalescent plasma will be labeled as per FDA guidance for the use of convalescent plasma in the treatment of COVID-19 patients. One unit (approximately 200mL) of convalescent plasma will be infused over 1 hour per standard institution protocols for the safe administration of blood products. Acetaminophen and Diphenhydramine are allowed as premedications consistent with institution standard practices.

Patients will be monitored in accordance with pre-established institutional guidelines.

6.2 Supportive Care for Clinical Deterioration While on This Study

Due to the possibility of clinical worsening in the interim after infusion, full supportive measures should be undertaken. This includes ventilator support, adequate volume expansion and pressure support. Antimicrobials are allowed in accordance with institution standard procedures.

6.3 Other Supportive Care

- Acetaminophen prior to plasma infusion is allowed.
- Diphenhydramine prior to or after plasma infusion is allowed in accordance with institutional procedural standards.
- Patients should receive *full supportive care*, including further transfusions of blood and blood products, antibiotics, antiemetics, etc., when appropriate.

6.4 Duration of Therapy

Patients should be considered enrolled in this clinical trial until discharge from the hospital or the following:

- Unacceptable adverse event(s),
- Patient decides to withdraw from the study, or
- General or specific changes in the patient's condition render the patient unacceptable for further treatment in the judgment of the investigator.

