1.0 OBJECTIVES

1.1 Primary Objectives:

To determine the therapeutic efficacy (response rate) of convalescent plasma infusion in patients at high risk for mortality when infected by SARS-CoV-2 (COVID-19). The primary endpoint will be determined as prevention of progression to severe or life threatening COVID-19 during the current hospitalization. The primary endpoint will be assessed at discharge and by evaluating if the patient experienced the following data elements: respiratory rate >30/min, Blood oxygen saturation <93%, partial pressure of arterial oxygen to fraction of inspired oxygen ration <300, or received a medical diagnosis of respiratory failure, septic shock or multiple organ dysfunction/failure. This will be captured from the daily physical exam/clinical assessment done as part of routine care. See table 1.

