6.5 Criteria for Removal from Study

Patients will be removed from study when any of the criteria listed in Section 6.4 apply. The reason for study removal and the date the patient was removed must be documented in the Case Report Form.

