10.0 MONITORING OF PATIENTS

Baseline evaluations are to be conducted the day of planned plasma infusion. At the discretion of the treating team, convalescent plasma may be held.

The recipient will be monitored for transfusion reaction in accordance with Norton Healthcare's policy which includes:

- Take vital signs (temp, pulse, blood pressure) prior to, 15 minutes after initiating and at the completion of the transfusion.
- RN, LPN, APRN, PA must remain with the patient unit the 15 min vital signs are performed and asses the patient periodically during the transfusion.

- Follow Norton Healthcare policy for Transfusion Reaction Protocol. Transfusion reactions will be reported per institutional policy.

Physical examination/clinical assessment will be done each day while on study.

Imaging will be completed at the discretion of the treatment team in response to clinical needs.

Laboratory testing as listed in Appendix 1 should be repeated every three days as part of clinical care. The frequency of overall testing should be at the discretion of the treating team.

Physical examination and laboratory recording should continue until patient no longer actively followed per section **6.4** and **6.5**.

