11.0 STATISTICAL CONSIDERATIONS

11.1 Study Design / Endpoints

This study uses a standard descriptive statistics for outcomes.

To determine the therapeutic efficacy (response rate) of convalescent plasma infusion in patients at high risk for mortality when infected by SARS-CoV-2 (COVID-19). The primary endpoint will be determined as prevention of progression to severe or life threatening COVID-19 during the current hospitalization. The primary endpoint will be assessed at discharge and by evaluating if the patient experienced the following data elements: respiratory rate $>30/\text{min}$, Blood oxygen saturation $<93\%$, partial pressure of arterial oxygen to fraction of inspired oxygen ration <300 , or received a medical diagnosis of respiratory failure, septic shock or multiple organ dysfunction/failure. This will be captured from the daily physical exam/clinical assessment done as part of routine care. See table 1.

The secondary objectives are to:

- Determine the immunologic effects of convalescent plasma infusion as measured by serial SARS-CoV-2 Ag levels through RT-PCR. This will be measured by CoV PCR collected at enrollment, day 7 and discharge.
- To measure normalization of laboratory parameters for risk as referenced in Appendix 2. Lab values outlined in appendix 2 will be documented every 3 days while the patient is hospitalized and we will evaluate labs from the time of convalescent plasma infusion to the time that lab value returns to within the institution's normal range.

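### Section 10 stops exam and lab recording when a patient is removed from study, but the primary endpoint runs to discharge and is taken from the daily assessment; the exposure is limited

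*Combined protocol and SAP*

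**What the plan says.** Section 10 ties the daily assessment to study participation: "Physical examination/clinical assessment will be done each day while on study". It also sets an end to recording: "Physical examination and laboratory recording should continue until patient no longer actively followed per section" 6.4 and 6.5.

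Section 6.4 lists three exits before discharge: an unacceptable adverse event, the patient's own withdrawal, and the case where "General or specific changes in the patient's condition render the patient unacceptable for further treatment in the judgment of the investigator". Section 6.5 gives the consequence, "Patients will be removed from study when any of the criteria listed in Section 6.4 apply", and adds that "The reason for study removal and the date the patient was removed must be documented in the Case Report Form".

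The primary endpoint in 1.1 has a longer window: "The primary endpoint will be determined as prevention of progression to severe or life threatening COVID-19 during the current hospitalization". It is judged at discharge. On the data source, 11.1 says "This will be captured from the daily physical exam/clinical assessment done as part of routine care". Section 6.6.1 likewise has the Appendix 2 elements collected for as long as the patient is in hospital.

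On who is analysed, section 9 says that every patient will be evaluated for response. Neither section 9 nor section 11 says how to classify a patient whose outcome is unknown.

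**The concern.** The window of the primary endpoint and the recording rule that feeds it end at different times for a removed patient. Two of the three early exits, an adverse event and a changed condition, are clinical, and either could be the beginning of a progression. If so, the patients whose recording stops early would not be a random subset.

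The response rate is the main result of a study with no comparison arm, so nothing else in the design would reveal a distortion. The direction depends on a rule the plan does not give:

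- If a removed patient with no recorded progression counts as a responder, any unseen progression raises the rate.
- If that patient counts as progressed, the rate is exact only when all such patients did progress, and too low otherwise.
- If such patients were dropped, the direction would depend on whether they progress more or less often than the rest.

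No hypothesis test is planned (11.2), so only the descriptive estimate is at stake.

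**Working it through.** The plan has no figure on this point to reproduce: it gives no removal rate, progression rate or precision target. The check is therefore a comparison of sections, followed by a simple bound.

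**Step 1. When each data stream ends for a patient removed before discharge**

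| Item | Stated end | Source |
|---|---|---|
| Primary endpoint window | End of the hospital stay | 1.1, 11.1 |
| Daily assessment | End of time on study | 10 |
| Exam and laboratory recording | Removal under 6.4/6.5 | 10 |
| Appendix 2 elements | While hospitalized | 6.6.1 |
| Serious adverse events, transfusion reactions | Discharge or death | 13 |
| Respiratory Status (daily entry) | None stated | Appendix 2 |
| Ventilator use | Covers the whole stay | Appendix 2 |
| Dated diagnoses after plasma | None stated | Appendix 2 |

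The second and third rows conflict with the first and fourth. The last four rows give partial cover.

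**Step 2. Which endpoint components remain exposed**

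Table 1 (section 15.0) has six criteria. Respiratory failure, septic shock and multiple organ dysfunction have dated fields in Appendix 2, and many such events would also be serious adverse events. The other three are numeric: respiratory rate, saturation and PaO2/FiO2. No text makes crossing one of those thresholds a serious adverse event in itself. The Respiratory Status block would hold the values, but no text expressly requires it after removal. The main gap is thus a progression met only on a numeric criterion after removal. The values would normally still be in the chart, so what is at risk is their abstraction.

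**Step 3. Bound on the response rate**

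Let n be the patients analysed, k those known to be responders, and m those removed whose outcome is still unknown after all the sources above have been used.

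- All unknown counted as responders: (k + m)/n
- All unknown counted as progressed: k/n
- Difference: (k + m)/n − k/n = m/n, whatever the progression rate

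The only input from the documents is the maximum accrual of 100 (11.2), taken here as all infused. The values of m, and n = 50, are assumptions.

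| m | Width at n = 100 | Width at n = 50 |
|---|---|---|
| 0 | 0 points | 0 points |
| 1 | 1 point | 2 points |
| 2 | 2 points | 4 points |
| 5 | 5 points | 10 points |

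Example with n = 100, m = 5 and an assumed 76 known responders: 76/100 = 76% if the five count as progressed, 76/95 = 80% if they are left out, and 81/100 = 81% if they count as responders.

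The width m/n is an identity that holds for any missing outcome. It shows scale and is not evidence that any outcome will be lost.

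**The case against.** The strongest reply is that the stated source is routine care, which does not stop when a patient leaves the study, and that the endpoint is a judgment made at discharge. The stop in section 10 names only examinations and laboratory values, whereas respiratory rate and saturation sit in a separate Appendix 2 block. Section 6.6.1 points to collection throughout the stay, and the outcome fields ask for the date of discharge or death alongside any withdrawal. This largely stands. It reduces the problem from lost data to chart data that nobody is clearly told to abstract, and it leaves the wording conflict in place.

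Three stronger readings are tempting, and the documents do not support them.

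- *Deteriorating patients are taken out, so the response rate is inflated by design.* Section 6.2 provides supportive care for patients who worsen while on study, which implies that they stay. One unit is given (6.1, 8.0), so further treatment has no clear object after infusion. That criterion may mainly concern plasma withheld beforehand, since section 10 notes that "At the discretion of the treating team, convalescent plasma may be held". Removal because of progression is possible but nowhere stated.
- *The endpoint cannot be determined after removal.* The partial cover set out above contradicts this for many events.
- *Removed patients may simply be left out of the denominator.* Section 9 points to an all-patient denominator. What is missing is narrower: the classification of an unknown outcome.

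An unacceptable adverse event remains a trigger that clearly applies after infusion. Much of what follows one would be caught by safety reporting to discharge or death, but a purely numeric progression might not be.

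**Conclusion.** The conflict between section 10 (with 6.4 and 6.5) and sections 1.1, 11.1 and 6.6.1 is real. It is a stated stopping rule for recording that can cut off endpoint data for reasons related to outcome, and so is more than missing detail. Its severity is minor. The exposure is mainly progression seen only in respiratory rate, saturation or PaO2/FiO2 after removal. The number of such patients is unknown and may be zero, in which case the response rate is unaffected.

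This rests on two readings: that removal under 6.5 is the point at which section 10 regards active follow-up as ended, and that the open-ended Appendix 2 fields are not expressly required after that point. If the sponsor already abstracts those fields to discharge for every patient, only the wording and the classification of unknown outcomes need attention.

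**What to change.** - Reconcile 6.4, 6.5 and 10 with 1.1, 11.1 and 6.6.1 so that removal for an adverse event or a changed condition does not end endpoint data collection. Treatment decisions are not affected.
- For all treated patients, abstract the existing Appendix 2 respiratory, diagnosis and ventilator fields from the routine chart to discharge or death, unless consent for data collection is withdrawn.
- In 11.1, keep the denominator consistent with section 9, and report separately the enrolled patients whose plasma was held.
- State the number with unknown outcome, with the removal reason already recorded under 6.5, and say that these patients are not counted as responders by default. Giving the rate with them counted each way is one convenient presentation.

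The cost is a short wording change and a little more chart abstraction for removed patients, with no new tests or visits. The response rate may come out less favourable.
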